Inclusion Criteria: Subjects with CF (medical record evidence of cystic fibrosis transmembrane conductance regulator mutation or sweat chloride test or nasal voltage difference, **and** 1 or more clinical findings of CF), age 12 or greater with an FEV₁ >30% predicted (within the last 14 days) and oxygen saturation \geq 90% on FiO₂ \leq 50%, admitted for an exacerbation, able to provide written informed consent or assent.

Exclusion Criteria: Pregnancy, hemoptysis more than 60 mL within the last 30 days, use of any investigational study drug within the last 30 days, initiation of hypertonic saline within the last 30 days, known intolerance to hypertonic saline, serum creatinine 2 mg/dl or more, active malignancy in the last year, on waiting list for lung transplantation, received a solid organ transplant, lack of FEV₁ data from the last 14 days and previous participation in this study.

Experimental Treatment: Aerosolized 15% xylitol, 5 ml twice a day for 2 weeks using Pari LC nebulizer with Vios compressor, (Pari Inc, Monterey, CA) . Xylitol crystals are

made as food additives by Danisco Cultor, USA. Aerosol solution is sterile, non-pyrogenic, preservative-free solution for inhalation made by UI Pharmaceuticals (Iowa City, IA).

Control Treatment: Hypertonic 7% saline (UIHC pharmacy) 4 ml twice a day for 2 weeks using the same kind of nebulizer.

Screening and Baseline Visit: On the day of admission for exacerbation, informed consent obtained in subjects whose admission spirometry (or spirometry within the last 14 days prior to admit date) shows an FEV₁ >30% predicted. Once consented, subjects will be randomized to either xylitol or saline group as per the randomization code previously generated by the statistician. Demographics, current medications use and the revised CF quality of life questionnaire (CFQ-R) will be completed. Spontaneously expectorated sputum will be collected and processed for cell count and cytokines and quantitative cultures. Blood will be collected for chemistry and liver function tests (LFT). Pregnancy test will be done in women. All medication use during hospitalization will be recorded. Treatment will begin the day after admission for an exacerbation. Results from spirometry that is routinely done twice a week for inpatients will be recorded. All spirometry testing will follow the 2005 American Thoracic Society guidelines.

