First dose pre and post spirometry: All subjects will undergo spirometry before and 20 minutes after the first study drug dose as follows.

Perform baseline spirometry and measure SpO₂. Multiply the patient's best FEV₁ by 0.80 to obtain 20% fall in FEV₁ value.

Premedicate subject with 4 puffs albuterol and wait 15-30 min.

Begin study drug nebulization.

Wait for 15-30 minutes and repeat spirometry and SpO₂.

Subject is excluded from the study if SpO₂ is <89% or FEV₁ declines by 20% or greater from baseline.

Administration: Subjects will take their routine inhaled medicines followed by chest physical therapy. All subjects will then receive 2-4 puffs of albuterol metered dose inhaler 15-30 minutes before the study drug. Finally the study drug will be inhaled. All empty, unused and partially used study drug containers will be tracked by the investigators. Subjects will be required not to use any new treatments if not medically indicated during the study period.

Day 14 follow-up: Subjects will undergo spirometry and sputum collection and answer CFQ-R questionnaire. Blood draw for LFTS and electrolytes will be done if not done for clinical reasons. If subjects are discharged prior to 14 days of xylitol use, nebulizer solutions will be sent home. They will be asked to keep a log of nebulizer use and bring back empty and unused vials on follow-up visit (Day 10-15, preferably day 14). They will undergo spirometry and sputum collection and questionnaire administration on that day. If subjects don't return on this day, they will have a phone follow-up for adverse events and compliance.

Phone follow-up: Week 1, Day 90 and Day 180 after discharge: Subjects will be contacted by phone at these time points to enquire about further pulmonary exacerbations, admissions, and other AEs.

In the event of bronchospasm: Subjects will alert the nurses or study team members. Nebulized bronchodilators will be immediately administered. Once symptoms resolve, they will undergo spirometry using a portable handheld spirometer by a trained user. If the subjects dropped FEV₁ by 20% or greater from their baseline, they will not receive further study drug. However, they will remain in the study for completion of data collection.

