However, if a subject consents to future use and some of their specimens have already been used for research purposes, the information from that research may still be used.

Statistical analysis: We plan to enroll a total of 60 subjects for this study. These subjects will be randomly assigned to the treatment (xylitol) and control (saline) groups, with a goal of 30 subjects in each group. Since this is a pilot safety study, it has been primarily powered to detect common adverse events. Assuming that the likelihood of a subject experiencing an adverse event is no less than 5%, a sample size of 30 subjects ensures 80% power towards event detection [16]. (In other words, with a group sample size of 30, the probability of observing at least one adverse event in the group is at least 80%.)

Study Performance

Accrual will be assessed on a monthly basis. We will examine the number of screened subjects, those meeting eligibility criteria, the number of persons consenting to participate and the number of randomized. The rate of accrual will be tracked versus the expected number to achieve the target of 60 participants randomized.

We will also track the completion number and proportion by time. The number of study terminations and reason for termination will be measured. The subject will undergo a spirometry and if the FEV₁ has declined by 20%, the subject will be terminated from the study.

Baseline

The composition of the study sample will be described in aggregate. Comparison of randomized participants of baseline characteristics will be analyzed using 2 sample t-test,

Wilcoxon rank sum test, and analysis of variance (ANOVA) as indicated by the type and characteristics of the variable.

Outcomes

To assess the adequacy of these group sample sizes for testing a trend in efficacy, we consider the outcome of log CFU. We assume an average density of colonization of 6.5 log CFU with a SD of 1.5 log CFU among CF subjects. To detect a reduction of 1.5 log CFU in the xylitol group with 80% power, the required sample size is 17 subjects per group. (This computation is based on a two-sided, two-sample t-test conducted at the 0.05 level of significance.) Data from all patients who have received at least one dose of the drug or placebo will be analyzed. Thus, the analysis will be based on intention to treat. All tests will be two-sided, and conducted using a significance level of 0.05.

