Stopping criteria: If any subject drops his/her FEV₁ % predicted by 20%, we will stop further exposures. If 3 subjects drop their FEV₁ by 20% the treatment assignment will be unblinded and they were all in the xylitol group, the study will be closed for further recruitment.

Safety Monitoring: Any unexpected fatal or life-threatening adverse event will be reported to the Food and Drug Administration (FDA) by phone, fax or email no later than 7 days of occurrence. Any other serious and unexpected adverse event associated with the use of xylitol will be reported to the FDA within 15 days of occurrence. Please see DSMP for a detailed safety plan.

REFERENCES

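### The 20% FEV₁ fall that stops study drug and feeds the three-subject closure rule has no single definition: qualifying readings, scale, reference reading and study status differ between sections

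*Combined protocol and SAP*

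**What the plan says.** Five places in the protocol deal with the event or with the readings that could show it.

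- **First dose pre and post spirometry.** The threshold is relative: staff multiply the subject's "best FEV₁ by 0.80 to obtain 20% fall in FEV₁ value". The consequence is: "Subject is excluded from the study if SpO₂ is <89% or FEV₁ declines by 20% or greater from baseline".
- **In the event of bronchospasm.** Spirometry follows once symptoms resolve. "If the subjects dropped FEV₁ by 20% or greater from their baseline, they will not receive further study drug". The next sentence adds: "However, they will remain in the study for completion of data collection".
- **Screening and Baseline Visit, and Day 14 follow-up.** "Results from spirometry that is routinely done twice a week for inpatients will be recorded". Day 14 spirometry is also planned. Neither section attaches a stopping action to these readings.
- **Study Performance, repeated under Risks.** "The subject will undergo a spirometry and if the FEV₁ has declined by 20%, the subject will be terminated from the study". Under Risks this follows bronchospasm; under Study Performance no trigger is given.
- **Stopping criteria.** "If any subject drops his/her FEV₁ % predicted by 20%, we will stop further exposures". Then the trial-level rule: "If 3 subjects drop their FEV₁ by 20% the treatment assignment will be unblinded and they were all in the xylitol group", in which case recruitment closes. No reading, time or reference value is named, and SpO₂ is not mentioned.

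Safety Monitoring refers to a DSMP for the detailed safety plan. It is not among the documents available here.

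**The concern.** The count of three is the only trial-level safety trigger stated in the protocol, and safety is the purpose of the trial. The same FEV₁ reading leads to different actions depending on which section staff follow, so the subjects who are stopped and the subjects who are counted need not be the same people.

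Two features raise the stakes. The protocol says that blinding is not assured because xylitol tastes sweet, so a decision on whether a given fall qualifies could be made by someone who can guess the arm. And the Outcomes section plans to analyse everyone who received at least one dose. Whether a subject with a large fall stays for follow-up or is terminated therefore decides whether later FEV₁ is available for exactly the subjects who matter most to the primary outcome.

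**Working it through.** **1. A stated figure to reproduce.** The protocol gives no operating characteristic for the closure rule. Its only event-probability figure is at least 80% for seeing one or more adverse events among 30 subjects at a 5% rate: 1 − 0.95^30 = 0.785, close to the stated value. Nothing below depends on it.

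**2. The rules side by side.**

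| Section | Reading that triggers it | Measure | Reference | Status afterwards |
|---|---|---|---|---|
| First dose | Post-dose check | Relative FEV₁ fall ≥20%, or SpO₂ <89% | Pre-dose baseline (0.80 × best FEV₁) | Excluded from study |
| Bronchospasm | Spirometry after symptoms resolve | FEV₁ fall ≥20% | Own baseline | Drug stopped, stays in study |
| Study Performance | Not stated | FEV₁ decline 20% | Not stated | Terminated from study |
| Risks | After bronchospasm | FEV₁ decline 20% | Not stated | Terminated from study |
| Stopping criteria, individual | Not stated, any subject | FEV₁ % predicted, 20% | Not stated | Exposures stopped |
| Stopping criteria, closure | Not stated | FEV₁, 20% | Not stated | Counted towards three |

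**3. Three cases run through the table.**

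- *Symptom-free 20% fall on a twice-weekly or Day 14 reading.* First dose and Bronchospasm: no action. Stopping criteria, read literally: a count, and a stop if dosing is continuing.
- *20% fall after bronchospasm.* Bronchospasm section: remains for data collection. Study Performance and Risks: terminated. This is a direct contradiction.
- *First-dose removal.* Stopping criteria does not say whether these subjects enter the count. An SpO₂-only removal does not meet its wording.

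**4. Scale.** If % predicted is read as a relative fall, it equals a relative fall in FEV₁, because the predicted value cancels. If it is read as percentage points, the threshold is baseline − 20 rather than 0.80 × baseline:

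| Baseline, % predicted | Relative: 0.80 × baseline | Points: baseline − 20 | Points drop as a relative fall |
|---|---|---|---|
| 40 | 32 | 20 | 20/40 = 50% |
| 60 | 48 | 40 | 20/60 = 33% |
| 80 | 64 | 60 | 20/80 = 25% |
| 100 | 80 | 80 | 20/100 = 20% |

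The two agree only at 100% predicted, and the gap is widest in the sickest subjects; entry requires FEV₁ above 30% predicted.

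**5. Illustration of the closure rule.** All inputs except the 60 subjects, the equal arms and the 20% threshold are assumptions. Changes are normal with mean μ and SD 10%, within-subject correlation ρ = 0.5, k qualifying readings per subject, and no drug effect. With c = (−20 − μ)/SD, the chance that one reading qualifies is Φ(c); for μ = 0, Φ(−2) = 0.0228. For k readings, p = 1 − ∫[1 − Φ((c − √ρ·z)/√(1−ρ))]^k φ(z) dz. The chance of at least three fallers is P(Binomial(60, p) ≥ 3). False closure multiplies this by (1/2)³ = 1/8, the chance that the first three are all on xylitol. Six readings means first dose, four twice-weekly and Day 14.

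| k | μ | p | Expected fallers, 60p | P(≥3) | False closure, P(≥3)/8 |
|---|---|---|---|---|---|
| 1 | 0 | 0.0228 | 1.4 | 15.6% | 2.0% |
| 6 | 0 | 0.0956 | 5.7 | 93.5% | 11.7% |
| 6 | +5% | 0.0298 | 1.8 | 26.6% | 3.3% |
| 3 | +5% | 0.0168 | 1.0 | 8.0% | 1.0% |
| 6 | +10% | 0.0071 | 0.4 | 0.9% | 0.1% |

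At six readings and μ = 0, SD 8% gives 3.3% and SD 12% gives 12.5%. With no arm difference, false closure cannot exceed 1/8 = 12.5% in this model.

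**The case against.** The best defence is that Stopping criteria merely summarises the earlier rules and that the DSMP may define the qualifying readings. Both are possible. It follows that one cannot say the trial lacks an operating definition; a reader might infer that, but the DSMP has not been seen. What survives is that the protocol text is wider than the rules it would be summarising and, on study status, contradicts itself. A definition in the DSMP would not remove that conflict.

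Three stronger readings are tempting and are not supported.

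- *That there are two competing closure counts.* Only Stopping criteria contains a count. The first-dose and bronchospasm rules are individual stops.
- *That leaving SpO₂ out of the closure count is a contradiction.* Individual removal criteria may properly be wider than a trial-level trigger. Desaturation removals are not lost either: Endpoints lists withdrawal as a safety assessment, and Study Performance records terminations with reasons.
- *That false alarms are near certain because three fallers are reached 93.5% of the time.* That figure needs zero mean change and six readings in every subject. These are inpatients treated for an exacerbation, the first-dose baseline precedes albuterol while the repeat follows it, and the protocol plans for discharge before 14 days. A mean rise and fewer readings are both plausible, and a +5% mean alone cuts 93.5% to 26.6%. Using one SD for a change within the hour and a change over two weeks is also a simplification, and the one-reading comparison leaves out any bronchospasm-triggered readings.

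**Conclusion.** The point holds as an inconsistency of definition. The protocol gives different actions for the same FEV₁ reading, leaves the scale and reference reading open in the section that governs closure, and contradicts itself on whether a subject stopped after bronchospasm stays in the study. These conclusions rest on the text alone.

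The scale ambiguity is material only if % predicted means percentage points. The effect on the closure rule cannot be sized from the documents, which give no SD, correlation or fall rate. Across the mean changes tried at six readings (SD 10%, correlation 0.5, no drug effect), false closure lies between about 0.1% and 11.7%. This shows that the choice of readings can matter, not how often the rule would misfire. It should be corrected; it is not evidence that the trial is unsafe.

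**What to change.** Reconcile Screening and Baseline Visit, First dose, Bronchospasm, Day 14 follow-up, Study Performance, Risks and Stopping criteria, together with the DSMP, to one written event definition. It should state:

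1. which spirometry readings qualify;
2. the reference reading;
3. the scale (relative fall in FEV₁, or points of % predicted);
4. study status and data collection after a stop;
5. whether first-dose exclusions, including SpO₂-only ones, enter the closure count.

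Apply it identically in both arms, and say explicitly wherever the individual stop and the closure count are meant to differ. The choice of clinical trigger is the sponsor's.

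Whatever is chosen, tabulate by arm every 20% FEV₁ fall and every SpO₂ removal, with the reading that showed it (first dose, bronchospasm, routine inpatient, Day 14), for whoever applies the closure rule.

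The cost is a wording amendment and one safety table. The readings are already planned, so no visits or tests are added.
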